5. GENERAL STATISTICAL CONSIDERATIONS

5.1. Reporting Conventions

Summary statistics for continuous variables include sample size (n), mean, standard deviation (SD), median, minimum, and maximum, also the 25th (Q1) and 75th (Q3) percentiles may be included in summary statistics. All mean, median and percentile values will be formatted to one more decimal place than the measured value and SD values will be formatted to two more decimal places than the measured value, if applicable. Minimum and maximum values will be presented to the same number of decimal places as the measured value. Frequency summary for categorical variables includes number and percentage. All percentages will be rounded to one decimal place. Number and percentage values will be presented as xx (xx.x%). All analysis and summary tables will have the population sample size for each treatment group in the column heading, if applicable. All p-values (2 sided) will be presented with 4 decimal places. All laboratory data will be reported using standard international (SI) units.

5.2. Study Phases and Analysis Periods

The study includes 4 phases:

1. Screening phase for up to 4 weeks (28 days)
2. Sixteen weeks, double-blind, placebo-controlled phase (apremilast 30 mg BID and placebo)
3. Sixteen weeks, active treatment phase (apremilast 30 mg BID)
 - Subjects randomized to apremilast continue apremilast treatment
 - Subjects randomized to placebo treatment switch to apremilast treatment in a blind manner
4. Four weeks post-treatment observational follow-up phase at any time the subject completes or discontinues the treatment

5.2.1. Analysis Periods

Per protocol specification, data summary and analysis will be provided for the following periods, if appropriate.

- Placebo-controlled Phase/Period

This period starts on the day of randomization (Week 0/Visit 2), and stops on below, whichever is later:

- (1) the day of Week 16/Visit 10 if the subject continued study treatment to the active treatment phase
- (2) the day of the discontinuation if the subject discontinued study treatment prior to or at Week 16/Visit 10
- (3) the last known study day if the subject is lost to follow-up prior to Week 16/Visit 10

CC-10004 (Apremilast)

Statistical Analysis Plan. Protocol CC-10004-PPP-001

The two treatment arms are apremilast 30 mg BID or Placebo.

- Active Treatment Phase/Period

This period starts on one day after the day of the first dose of apremilast at Week 16/Visit 10, and stops on either below.

- (1) the day of Week 32/Visit 14
- (2) the day of the discontinuation if the subject discontinued prior to or at Week 32/Visit 14
- (3) the last known study day if the subject lost to follow-up prior to Week 32/Visit 14 during the phase

The two treatment arms are 30 mg BID/30 mg BID, and Placebo/30 mg BID.

For safety analysis, the period starts on the day of the first dose of apremilast in the period.

- Observational Follow-up Phase/Period

Subjects who complete or discontinue the study treatment, will be followed up for 28 days after last dose of IP.

For adverse event analysis, data from the first 28 days after the last dose of IP will be included in the precedent treatment phase and data after the 28 days will be presented separately.

- Apremilast-exposure Period

This period starts on the date of either:

- (1) the first dose of IP following randomization (Week 0/Visit 2) for subject who are treated with apremilast from Week 0
- (2) the first dose of IP from the IP dispensed at Week16/Visit 10 for subjects who were originally treated with placebo and are switched to apremilast at Week 16

This period stops on either: (1) data restriction date; or (2) the end of the study.

During the apremilast-exposure period, data are presented by treatment sequence, i.e., Placebo/30 mg BID, 30 mg BID as Initiated, and a total column of 30 mg BID as Treated.

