During Weeks 16 to 32, the IP will remain blinded, to prevent study personnel and subjects from knowing the IP assignment in the double blind, placebo-controlled Phase (Week 0 to 16) and to maintain the blind regarding the initial treatment assignment, all subjects will receive dose titration cards at Visit 10 (Week 16). Although only subjects initially randomized to placebo will be dose titrated during their first week of the active treatment phase, all subjects entering the active treatment phase will receive identically-appearing titration/treatment cards as shown in [Table 7](#).

Please refer to local apremilast prescribing information for more details on available formulations, preparation, storage conditions, the approved indications, known precautions, warnings, and adverse reactions of apremilast (see current version of Prescribing Information). The apremilast dosing schedule and dose adjustments to be followed for this study are described in [Section 7.3](#).

Additional information may be included on the label as needed or applicable. Label(s) for IP will contain information as required per local health authority.

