5.4. Time points

Time points in all analyses are based on the remapped visits/study weeks using the following visit mapping algorithm, which may not be the same as the visits/study weeks as recorded in the database.

All visit-based data, except for those with the recorded visit being a follow-up visit, will be assigned to analysis visits based on study day (the date of assessment/collection relative to the reference date) and the defined analysis visit windows as below, rather than the recorded visit. The only exception is that the data with a recorded visit being a follow-up visit will be assigned to the analysis visit corresponding to the follow-up visit.

Table 4 Table for Visit Mapping for by Time Point Analysis

Analysis Visit	Target Day	Analysis Window
Week 0 (Visit 2: Baseline)	1	≤ 1
Placebo-controlled Period		
Week 2 (Visit 3)	15	2 – 21
Week 4 (Visit 4)	29	22 – 35
Week 6 (Visit 5)	43	36 – 49
Week 8 (Visit 6)	57	50 – 63
Week 10 (Visit 7)	71	64 – 77
Week 12 (Visit 8)	85	78 – 91
Week 14 (Visit 9)	99	92 – 105
Week 16 (Visit 10)	113	106 – End of the Period
Active Treatment Period		
Week 20 (Visit 11)	141	One day after the first apremilast dosing day on Visit 10* – 154
Week 24 (Visit 12)	169	155 – 182
Week 28 (Visit 13)	197	183 – 210
Week 32 (Visit 14)	225	211 – End of the Period

* The first apremilast dosing day on Visit 10 shall be used for adverse event data

Time points in the analyses or summaries of efficacy data over time include the scheduled study weeks per protocol, the end of a study phase, and the post-treatment observational follow-up phase when applicable. It is possible that multiple assessment values will fall into the same visit window. The following rule may be used to select the unique value for that analysis visit:

Among all assessments in the same visit window for the analysis visit, select the value with the assessment date closest to the target day of the analysis visit;

1. If the relative days from 2 assessments are equally close to, but on different sides of the target day, then the latter assessment will be used for that analysis visit;
2. If multiple assessments are available on the same relative day, then the highest (worst) value of these assessments will be used for that relative day.

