9.2. Treatment Compliance

For treatment compliance, descriptive statistics will be provided. The treatment compliance (%) for each subject will be computed as 100 times the total number of tablets taken (the total number of tablets dispensed minus the total number of tablets returned minus the number of tablets lost) over the period divided by the intended total number of tablets that should have been taken over the same period.

It is assumed that from the first through the last IP administered date, a subject takes the first 5 rows of tablets (6 tablets per row/day) on each complete blister card before taking the remaining rows (2 tablets per row/day), and completes the first 28 rows, skips rows 29-33 (5-day extra supply) and starts a new blister card, in case the subject visit at the planned date. It is also assumed that a subject takes the full day's tablets from a new blister card on a study drug dispense date.

The intended total number of tablets is calculated as

$$\text{The intended total number of tablets} = \begin{cases} 6 \times n & (\text{when } n < 6) \\ 30 + 2 \times (n - 5) & (\text{when } n \geq 6) \end{cases}$$

where n denotes the number of days between the returned date and dispensed date (ie, the date of return minus the date of dispense).

Summary statistics for compliance rate (%) will be provided. A frequency summary of compliance rate will also be presented with the following categories: < 75%, ≥ 75% to ≤ 100%, > 100% to ≤ 120% and > 120%.

CC-10004 (Apremilast)

Statistical Analysis Plan. Protocol CC-10004-PPP-001

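### For adverse events the SAP moves the start of the apremilast period onto Visit 10 day but does not move the end of the placebo-controlled period, so first-apremilast-day events in placebo switchers also fall under placebo

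*SAP*

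**What the plan says.** SAP 5.2.1 defines the analysis periods. For a subject who goes on to the active phase, the placebo-controlled period stops on "the day of Week 16/Visit 10 if the subject continued study treatment to the active treatment phase". The general rule for the active period fits this: "This period starts on one day after the day of the first dose of apremilast at Week 16/Visit 10". A separate sentence then changes the start for safety: "For safety analysis, the period starts on the day of the first dose of apremilast in the period". For placebo subjects the apremilast-exposure period starts on the date of "the first dose of IP from the IP dispensed at Week16/Visit 10 for subjects who were originally treated with placebo".

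The footnote to Table 4 in SAP 5.4 repeats the earlier start: "The first apremilast dosing day on Visit 10 shall be used for adverse event data". The Week 16 window in that table still runs to the end of the placebo-controlled period.

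On the timing of the first dose, protocol 7.1 has the switch cards handed out at Visit 10. SAP 9.2, on compliance, says: "It is also assumed that a subject takes the full day's tablets from a new blister card on a study drug dispense date".

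SAP 17.2.1 (Table 6) covers incomplete onset dates in subjects who began on placebo. If the known part of the date matches the month of the first apremilast dose, or its year when the month is missing too, the onset is set to the date of that dose.

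SAP 11 and 11.1 ask for adverse event incidence and exposure-adjusted rates by period. They contain no rule that gives an event to one period only.

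**The concern.** The start of the later period was moved for adverse events, and the end of the earlier one was not. With same-day dosing, Visit 10 day belongs to both. In the placebo arm that is the first day on apremilast, so an event that begins after the new card is started is reported under placebo in Weeks 0–16. In the apremilast arm the day is apremilast under either period, so nothing is reported under the wrong drug there.

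Weeks 0–16 is the only randomised safety comparison, and safety against placebo is the secondary objective. The plan expects gastrointestinal effects when apremilast is started, which is why it titrates. The misplacement also departs from the SAP's own principle of analysing safety by the treatment received (SAP 5.5).

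**Working it through.** **Boundary day.** Day 1 is the first dose, so Week 16 falls on Day 16 × 7 + 1 = 113, which matches SAP 4.2.4.1.2 and Table 4.

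**Is the end day included?** Yes. The Week 16 assessment takes place on that day and must fall in the placebo-controlled period, and the general active period starts only on the following day.

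**Overlap.** Write V for the study day of Visit 10 and F for the day of the first dose from the Visit 10 supply. For a subject who continues:

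- placebo-controlled period: Days 1 to V
- active period, general rule: from Day F + 1
- active period, safety rule: from Day F

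| V = 113 | General rule: shared days | Adverse event rule: shared days | Adverse event rule: days in neither period |
|---|---|---|---|
| F = 113 (same day) | none | Day 113 | none |
| F = 114 | none | none | none |
| F = 115 | none | none | Day 114 |

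Moving V to 111 or 115, the limits of the ±2-day visit window, shifts the shared day to 111 or 115 and changes nothing else. The overlap therefore arises if and only if F = V. For placebo subjects the apremilast-exposure period also starts on Day F, so the same result holds for it.

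**Is F = V the normal case?** The Table 4 footnote locates the first apremilast dosing day on Visit 10, and the active-period definition does the same. SAP 9.2 assumes dosing on the dispensing date, though only for tablet counts.

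**Partial dates.** Table 6 sends them to Day F. When F = V they land on the shared day, unless a complete end date before Day F pulls the onset back. Events that the SAP chooses to attribute to apremilast then also meet the placebo-period definition.

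**Size.** The documents give no first-day event rate. Assume that 40 of the 43 placebo subjects switch on Visit 10 day. The largest addition to the placebo any-event row is 40 × rate:

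| Assumed first-day rate | Subjects added, at most | As a share of 43 |
|---|---|---|
| 2% | 40 × 0.02 = 0.8 | 0.8 / 43 = 1.9 points |
| 5% | 40 × 0.05 = 2 | 2 / 43 = 4.7 points |
| 10% | 40 × 0.10 = 4 | 4 / 43 = 9.3 points |

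These are upper bounds. SAP 11 counts a subject once per row, so anyone with an earlier event in Weeks 0–16 adds nothing to the any-event row. Any single preferred term receives only part of the total. Partial dates are not in these figures.

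In time, the shared day is at most 43 of 43 × 113 = 4,859 placebo subject-days, or 0.9%. That share would measure the effect only if the day were an average one. It is the first day of titration.

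**After the fix.** Ending the period on Day F − 1 leaves no shared day and no unassigned day in any row above. On schedule, the adverse event periods become Days 1–112 and Day 113 onward.

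**The case against.** The strongest reply is that the SAP already shows which period should own the day. The safety sentence, the Table 4 footnote and the imputation principle in SAP 17.2.1 all place such events with apremilast, so a careful programmer might take them out of the placebo period. That is a fair account of the intent. It does not settle the analysis, because the stated end date still includes the day and no rule removes the event.

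The dosing premise is conditional. SAP 9.2 makes an assumption for compliance and does not instruct subjects when to dose. A first dose one day later removes the overlap. This stands as a qualification.

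The fix has an error of its own. Visit 10 includes a complete physical examination, laboratory tests, vital signs and a psychiatric evaluation. A finding from these with onset recorded that day, before the new card is started, belongs to the randomised phase, yet would be assigned to the apremilast period. The same abnormality could then be a placebo-phase laboratory value and an apremilast-period event. This cost is real, and the documents do not allow the two errors to be compared in size. The direction is the one the SAP has already chosen in its footnote and imputation principle.

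Two stronger readings are tempting and do not hold. A reader might infer that reporting an event in both sets of tables is itself double counting. It is not: the apremilast-exposure tables overlap the Weeks 0–16 tables by design, since for subjects who start on apremilast the exposure period begins at Week 0. A reader might also set the percentages above against the 5% cut-off for most frequent events. That cut-off is applied by system organ class or preferred term, while the percentages are bounds for any event, so they cannot be compared.

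**Conclusion.** The point holds. As written, the SAP places adverse events that begin on placebo subjects' first apremilast day in the placebo column of the Weeks 0–16 tables whenever that dose is taken on the day of Visit 10. Partial dates imputed to that dose go the same way. The misattribution is one-sided and can only narrow the apparent safety difference.

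Its size cannot be derived from the documents. With 40 switchers and first-day rates of 2% to 10%, all assumed, the any-event row gains at most 0.8 to 4 subjects. Protocol Table 7 shows a single 10 mg active tablet on the first titration day, so the lower end may be closer.

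The consequence is limited. Safety is descriptive with no inferential testing, and the primary efficacy analysis does not use this boundary. The change should still be made, because this is the only randomised safety comparison and the correction is simple.

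**What to change.** Add one sentence to SAP 5.2.1: for adverse events, in both arms, the placebo-controlled period for subjects who continue into the active phase ends on the day before the first dose from the investigational product dispensed at Visit 10. State that Visit 10 day stays in the placebo-controlled period for efficacy, laboratory and vital-sign data. Give the Week 16 window in Table 4 the same limit for adverse events, so that the footnote and the period definition agree.

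The cost is that sentence, the matching table note and one date condition in the adverse event dataset. The same condition closes the one-day gap for a subject who first doses two days after Visit 10. The downside, to be stated in the SAP, is that an event starting on Visit 10 day before the first dose, including one found at that visit's assessments, goes to the apremilast period.

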5.3. Baseline Definitions

Baseline is defined as the last value measured on or before the day of the first IP.

For efficacy analyses and summary of baseline disease characteristics, baseline is defined as the last value measured on or before the day of the first dose of IP. For the summaries of laboratory parameters, and vital signs parameters, baseline is defined as the last value measured on or before the day of the first dose of IP in the summaries for the placebo-controlled phase, and defined as the last value measured on or before the day of the first apremilast dose for subjects initially randomized to placebo and switched to apremilast in the summaries for the apremilast exposure period.

CC-10004 (Apremilast)

Statistical Analysis Plan. Protocol CC-10004-PPP-001

5.4. Time points

Time points in all analyses are based on the remapped visits/study weeks using the following visit mapping algorithm, which may not be the same as the visits/study weeks as recorded in the database.

All visit-based data, except for those with the recorded visit being a follow-up visit, will be assigned to analysis visits based on study day (the date of assessment/collection relative to the reference date) and the defined analysis visit windows as below, rather than the recorded visit. The only exception is that the data with a recorded visit being a follow-up visit will be assigned to the analysis visit corresponding to the follow-up visit.

Table 4 Table for Visit Mapping for by Time Point Analysis

Analysis Visit	Target Day	Analysis Window
Week 0 (Visit 2: Baseline)	1	≤ 1
Placebo-controlled Period		
Week 2 (Visit 3)	15	2 – 21
Week 4 (Visit 4)	29	22 – 35
Week 6 (Visit 5)	43	36 – 49
Week 8 (Visit 6)	57	50 – 63
Week 10 (Visit 7)	71	64 – 77
Week 12 (Visit 8)	85	78 – 91
Week 14 (Visit 9)	99	92 – 105
Week 16 (Visit 10)	113	106 – End of the Period
Active Treatment Period		
Week 20 (Visit 11)	141	One day after the first apremilast dosing day on Visit 10* – 154
Week 24 (Visit 12)	169	155 – 182
Week 28 (Visit 13)	197	183 – 210
Week 32 (Visit 14)	225	211 – End of the Period

* The first apremilast dosing day on Visit 10 shall be used for adverse event data

Time points in the analyses or summaries of efficacy data over time include the scheduled study weeks per protocol, the end of a study phase, and the post-treatment observational follow-up phase when applicable. It is possible that multiple assessment values will fall into the same visit window. The following rule may be used to select the unique value for that analysis visit:

Among all assessments in the same visit window for the analysis visit, select the value with the assessment date closest to the target day of the analysis visit;

1. If the relative days from 2 assessments are equally close to, but on different sides of the target day, then the latter assessment will be used for that analysis visit;
2. If multiple assessments are available on the same relative day, then the highest (worst) value of these assessments will be used for that relative day.

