### **6.7.3.2. EQ-5D**

EQ-5D-5L is also a general and comprehensive QoL questionnaires which assesses the subject status on the visit day. See [Appendix I](#).

The EQ-5D is a generic health status measure composed of a descriptive system which comprises the following 5 dimensions: mobility, self-care, usual activities, pain/discomfort and anxiety/depression, and a VAS asking individuals to rate their own health. A lower utility index and VAS score indicates more severe disease.

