4.2.4.8. EQ-5D

EQ-5D is a general and comprehensive QoL questionnaires which assesses the subject status on the visit day. The EQ-5D is a generic health status measure composed of a descriptive system which comprises the 5 dimensions (mobility, self-care, usual activities, pain/discomfort and anxiety/depression) each of which has 5 levels: no problems, slight problems, moderate problems, severe problems and unable, and a VAS asking individuals to rate their own health on a vertical, visual analog scale where the endpoints are labeled 'Best imaginable health state' (score of 100) and 'Worst imaginable health state' (score of 0). EQ-5D health states will be converted into a single index value by applying country specific value set ([Ikeda, 2015](#)).

CC-10004 (Apremilast)

Statistical Analysis Plan. Protocol CC-10004-PPP-001

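### The same-day duplicate rule in SAP 5.4 treats the highest value as the worst, which is backwards for the EQ-5D index and EQ-5D VAS

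*SAP*

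**What the plan says.** SAP 5.4 first maps data to analysis visits. Its opening is general: "Time points in all analyses are based on the remapped visits/study weeks using the following visit mapping algorithm", and "All visit-based data, except for those with the recorded visit being a follow-up visit, will be assigned to analysis visits based on study day". The only exception given is for recorded follow-up visits.

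The paragraph that deals with several values in one window begins more narrowly: "Time points in the analyses or summaries of efficacy data over time include the scheduled study weeks per protocol". It then introduces the selection rule in permissive terms: "The following rule may be used to select the unique value for that analysis visit". The value closest to the target day is taken. Item 1 settles ties on either side of the target day in favor of the later one. Item 2 deals with several values on one day: "then the highest (worst) value of these assessments will be used for that relative day". No measure is excepted.

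On the direction of EQ-5D, Protocol 6.7.3.2 says: "A lower utility index and VAS score indicates more severe disease". SAP 4.2.4.8 agrees for the VAS, with 100 at the best end and 0 at the worst.

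**The concern.** Item 2 is evidently meant to be conservative, since the parenthesis says so. It carries out that intent with the word highest, which works only where a larger number means worse disease. For EQ-5D the two words point to different records. A programmer who follows the first takes the healthier value, and one who follows the second takes the less healthy value. SAP section 2 says the plan exists to fix such choices before unblinding, and here it does not.

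EQ-5D falls under the rule however its scope is read. SAP Table 3 lists the change in index and VAS among the exploratory efficacy endpoints at Weeks 8, 16, 24 and 32, and SAP 10.3.2 summarizes both by time point.

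If the rule also reaches laboratory data, a low count that meets a Table 7 criterion could be replaced in a by-visit table by a same-day value that does not. Weight raises the same question. SAP 11.4 summarizes it by visit, and Protocol 6.5.7 is concerned with weight loss.

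**Working it through.** The plan gives no figure on this point, so the check is to compare the highest value with the worst value on each scale.

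**Step 1. Direction of each score.** The same-day pairs below are assumed, for illustration only.

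| Measure | Worse direction (source) | Pair | Highest | Worst | Agree? |
|---|---|---|---|---|---|
| PPPASI | higher (SAP 4.2.4.1) | 14, 18 | 18 | 18 | yes |
| PGA | higher (SAP 4.2.4.5) | 2, 3 | 3 | 3 | yes |
| Symptom VAS | higher (SAP 4.2.4.6) | 40, 55 | 55 | 55 | yes |
| DLQI | higher (SAP 4.2.4.7) | 6, 9 | 9 | 9 | yes |
| EQ-5D VAS | lower (Protocol 6.7.3.2, SAP 4.2.4.8) | 60, 80 | 80 | 60 | no |
| EQ-5D index | lower (Protocol 6.7.3.2) | 0.70, 0.85 | 0.85 | 0.70 | no |

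PPSI (SAP 4.2.4.3) and modified PPPASI (SAP 4.2.4.2) are also scored with higher as worse, so the rule is right for them.

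**Step 2. Laboratory analytes, if the rule covers them.** SAP Table 7 has 23 analytes:

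- 4 with only a low criterion: albumin, leukocytes, segmented neutrophils, lymphocytes. Highest is the least abnormal value.
- 7 with both a low and a high criterion: sodium, potassium, glucose, calcium, phosphate, platelets, hemoglobin. Highest is worst for a high abnormality and best for a low one.
- 12 with only a high criterion. Highest is worst.

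Check: 4 + 7 + 12 = 23. As an assumed example, take same-day neutrophil values of 1.3 and 1.8 against the criterion of below 1.5. The rule keeps 1.8, and the value shown for that visit no longer meets the criterion.

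**Step 3. Size for EQ-5D.** The protocol plans 43 subjects per arm. Suppose all 43 have a value and one has a same-day pair as in Step 1. Choosing the other record moves the arm mean by

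- EQ-5D VAS: (80 − 60) / 43 = 0.47 points on a 0 to 100 scale;
- EQ-5D index: (0.85 − 0.70) / 43 = 0.0035.

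The documents do not say how many such pairs to expect.

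**Step 4. Which outputs depend on the selected value.**

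- Primary endpoint: PPPASI is higher-is-worse, so the rule does what it intends.
- EQ-5D: by-time-point summaries. The sentence in SAP 10.3.2 that assigns the repeated-measures model does not name EQ-5D.
- Laboratory data, if covered: the summaries over time and the by-visit shifts in SAP 11.3. The shift to the worst post-baseline value is defined separately there and allows for low as well as high abnormality.

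**The case against.** The word in parentheses already states the intent, and a sensible programmer would honor it. The rule is also permissive. Neither point removes the conflict for EQ-5D: the sentence still names two different records, and permission to use a rule does not say which one to take.

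The objection is stronger on frequency. EQ-5D is a self-completed questionnaire scheduled once at each of five visits in Protocol Table 5, with no planned repeat. Unscheduled laboratory tests are allowed, but the tests go to a central laboratory, so a retest prompted by a result would probably fall on a later day, where the closest-to-target rule applies. That last step is inference, but it is reasonable. Same-day duplicates are likely to be rare.

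It is also strong on scope. The general sentences in SAP 5.4 govern assignment to visits, while the paragraph containing the duplicate rule opens with efficacy data. Against that, SAP 11.3 needs one laboratory value per visit, and the SAP gives no other rule for choosing between same-day values. The laboratory part is therefore a question of scope that the SAP should settle.

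A reader might go further and infer that the rule picks the wrong laboratory value whenever a blood draw is repeated, or that platelets and hemoglobin are reversed. Table 7 does not support either. Highest is worst for the 12 high-only analytes, and platelets and hemoglobin have criteria on both sides.

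**Conclusion.** The wording error is certain for the EQ-5D index and EQ-5D VAS and rests only on the documents' own scale directions. For laboratory data it is conditional on the rule applying to them: reversed for 4 of 23 analytes, unreliable for 7, correct for 12. The same condition applies to vital signs.

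The effect is small. It arises only when a same-day pair falls on the day chosen for an analysis visit, and it touches exploratory or descriptive by-visit output. The primary analysis, sample size and power are unchanged.

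Two stronger conclusions are tempting and not supported. One is that the rule biases the treatment comparison. It applies alike to both arms, EQ-5D is exploratory, SAP section 11 has no inferential safety testing, and nothing shows that duplicates would differ by arm. The other is that it would hide laboratory safety signals. SAP 11.3 provides the separate worst-value shift and lists all laboratory data with out-of-range values flagged. Its marked-abnormality incidence uses its own low and high criteria, and nothing there confines that to the value selected per visit.

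**What to change.** In SAP 5.4 item 2, replace the highest (worst) wording with: the worst value in the direction of that measure, meaning lowest for the EQ-5D index and EQ-5D VAS and highest for the other efficacy scores.

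Then state whether the rule covers laboratory and vital sign data. If it does, give a direction for each parameter and a tie-break for two cases: both same-day values in range, and one low with one high. An instruction to take the value furthest outside the reference range would not be enough, because it selects nothing when both values are in range.

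The EQ-5D part costs one sentence and a direction flag in the programming. If laboratory and vital sign data are covered, a short table of directions and tie-breaks is needed as well. No new data are required.
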